7.2. Clinical Laboratory

Mean and mean change from baseline in clinical laboratory data from central laboratory (including parameters for assessment of hepatic and renal monitoring) listed in [Table 4](#) will be summarized by analysis visit, as well as the last assessment during the double-blind period. In addition, shift tables for each laboratory parameters from baseline to each of the post-baseline visit, and to last assessment will be provided.

Table 4: Clinical Laboratory Parameters

| Type | Parameters |
|--------------|--|
| Hematology | leukocytes, basophils, basophils/leukocytes, eosinophils, eosinophils/leukocytes, lymphocytes, lymphocytes/leukocytes, monocytes, monocytes/leukocytes, neutrophils, neutrophils/leukocytes, hemoglobin, hematocrit, erythrocytes, platelets |
| Biochemistry | sodium, potassium, bicarbonate, blood urea nitrogen, creatinine, magnesium, calcium, uric acid, glucose, total protein, bilirubin (direct and indirect), aspartate aminotransferase, alanine Aminotransferase, gamma glutamyl Transferase, creatine kinase, alkaline phosphatase, total cholesterol, lactate dehydrogenase (LDH), high-density lipoprotein (HDL), low-density lipoprotein (LDL), triglycerides, and cystatin C |
| Urinalysis | pH, glucose, ketones, blood, protein |

All post-baseline clinical laboratory results will be graded according to CTCAE severity grade (criteria in [Appendix 4](#)), when applicable. For parameters graded according to CTCAE severity, the CTCAE grades increase from baseline to Grade 2 or higher grade will be considered as clinically significant (CS) and the incidence will be summarized for as-treated population.

The incidence of all post-baseline specific renal laboratory parameters provides information on action to be taken for study drug will be summarized.

Table 5: Renal Monitoring Parameters and Actions to Be Taken

| Laboratory Parameter | Stop Study Drug Immediately, Confirm Abnormal Value, and Then Start Work-Up | Stop Study Drug After Confirming ^a Abnormal Value, and Then Start Work-Up |
|----------------------|---|--|
| Serum cystatin C | >2.00 mg/L | >1.33 - 2.00 mg/L |
| Serum creatinine | ≥ Grade 2 (≥1.5 x ULN for age) | Grade 1 (>ULN - 1.5 x ULN for age) |
| Serum BUN | ≥3.0 x ULN | ≥1.5 - 3.0 x ULN |

Abbreviations: BUN, blood urea nitrogen; ULN, upper limit of normal

a Laboratory abnormalities may be confirmed immediately or at the next scheduled clinic visit based on investigator judgment.

Laboratory abnormality related to elevated liver function test will also be summarized for all post-baseline assessments according to [Table 6](#).

Table 6: Criteria for Elevated Liver Function Test

| Category | Criteria |
|-------------------------------|---|
| Elevated Aminotransferases | 
 ALT >3xULN AST >3xULN ALT or AST >3xULN |
| Elevated Bilirubin | 
 Total Bilirubin >2xULN AST or ALT >3xULN and Total Bilirubin >2xULN |
| Elevated Alkaline Phosphatase | 
 AP >1.5xULN AST or ALT >3xULN, Total Bilirubin >2xULN, and AP >1.5xULN |

Abbreviations: ALT, alanine aminotransferase; AST, aspartate aminotransferase; AP, alkaline phosphatase; ULN, upper limit of normal

A listing of all CS abnormal laboratory values, renal laboratory abnormal values, and elevated liver function test will be provided.

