In the event of an inhibition of body height increases that is unacceptable to the subject/family, the following interventions are recommended:

- Corticosteroid dosage should not be increased to adjust for increases in body weight
- Reassurance and support should be provided. Counseling from a child psychologist should be considered.
- If the failure to gain height remains unacceptable to child/family, dosage reductions of ≤ 5 mg total dose for prednisone (≤ 6 mg total dose for deflazacort) at ~6-week intervals can be considered.

- Every attempt should be made to avoid stopping corticosteroids solely for failure to gain height; if the subject/family demands that corticosteroids be stopped, see Section D below for procedures for withdrawal of corticosteroids.

Hyperglycemia or Glycosuria

Evidence of fasting hyperglycemia or $\geq 1+$ glycosuria persisting for ≥ 6 weeks should prompt the following interventions:

- Institute monitoring of glycosylated hemoglobin (hemoglobin A1c) to evaluate for evidence of chronic hyperglycemia.
- If hyperglycemia or glucosuria is only episodic and chronic hyperglycemia is not present by hemoglobin A1c, corticosteroids should not be increased to adjust for increases in body weight.
- If chronic hyperglycemia is present by hemoglobin A1c, consultation should be arranged with an endocrinologist regarding diagnostic evaluation and potential intervention for hyperglycemia
- If hyperglycemia persists and corticosteroid dose reduction is warranted, dosage reductions of ≤ 5 mg total dose for prednisone (≤ 6 mg total dose for deflazacort) at ~ 6 -week intervals can be considered.
- If the endocrinologist recommends corticosteroid discontinuation, corticosteroids may be stopped. See Section D below for procedures for withdrawal of corticosteroids.

Hypertension

Evidence of substantial hypertension (blood pressure elevation at 99th percentile + 15 mmHg for age) persisting for ≥ 6 weeks should prompt the following interventions:

- Corticosteroids should not be increased to adjust for increases in body weight. Dietary recommendations (weight reduction/sodium reduction) should be considered.

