| Hypocalcemia | Corrected serum calcium of <LLN - 8.0 mg/dL; <LLN - 2.0 mmol/L; Ionized calcium <LLN - 1.0 mmol/L | Corrected serum calcium of <8.0 - 7.0 mg/dL; <2.0 - 1.75 mmol/L; Ionized calcium <1.0 - 0.9 mmol/L; symptomatic | Corrected serum calcium of <7.0 - 6.0 mg/dL; <1.75 - 1.5 mmol/L; Ionized calcium <0.9 - 0.8 mmol/L; hospitalization indicated | Corrected serum calcium of <6.0 mg/dL; <1.5 mmol/L; Ionized calcium <0.8 mmol/L; life-threatening consequences | Death |
| Creatinine increased | >ULN - 1.5 x ULN | >1.5 - 3.0 x baseline; >1.5 - 3.0 x ULN | >3.0 x baseline; >3.0 - 6.0 x ULN | >6.0 x ULN | |
| Hyperglycemia | Abnormal glucose above baseline with no medical intervention | Change in daily management from baseline for a diabetic; oral antiglycemic agent initiated; workup for diabetes | Insulin therapy initiated; hospitalization indicated | Life-threatening consequences; urgent intervention indicated | Death |

| AE Term | Grade 1 | Grade 2 | Grade 3 | Grade 4 | Grade 5 |
|------------------|---|--|---|---|----------------|
| Hypoglycemia | <LLN - 55 mg/dL; <LLN - 3.0 mmol/L | <55 - 40 mg/dL; <3.0 - 2.2 mmol/L | <40 - 30 mg/dL; <2.2 - 1.7 mmol/L | <30 mg/dL; <1.7 mmol/L; life-threatening consequences; seizures | Death |
| Hypophosphatemia | <Laboratory finding only and intervention not indicated | Oral replacement therapy indicated | Severe or medically significant but not immediately life-threatening; hospitalization or prolongation of existing hospitalization indicated | life-threatening consequences | Death |
| Hyperkalemia | >ULN - 5.5 mmol/L | >5.5 - 6.0 mmol/L; intervention initiated | >6.0 - 7.0 mmol/L; hospitalization indicated | >7.0 mmol/L; life-threatening consequences | Death |
| Hypokalemia | <LLN - 3.0 mmol/L | <LLN - 3.0 mmol/L; symptomatic; intervention indicated | <3.0 - 2.5 mmol/L; hospitalization indicated | <2.5 mmol/L; life-threatening consequences | Death |
| Hyponatremia | <LLN - 130 mmol/L | 125-129 mmol/L and asymptomatic | 125-129 mmol/L symptomatic; 120-124 mmol/L regardless of symptoms | <120 mmol/L; life-threatening consequences | Death |
| Hypernatremia | >ULN - 150 mmol/L | >150 - 155 mmol/L; intervention initiated | >155 - 160 mmol/L; hospitalization indicated | >160 mmol/L; life-threatening consequences | Death |
| Hyperuricemia | >ULN without physiologic consequences | - | >ULN with physiologic consequences | life-threatening consequences | Death |

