7.1.1. Adverse Events of Special Interest (AESI)

The following TEAEs are considered as the adverse events of special interest (AESI), and will be summarized by AESI Category and PT for each treatment group:

Table 3: Adverse Events of Special Interest (AESI)

| AESI Category | Definition |
|---|---|
| Potential of aminoglycoside renal toxicity | 
 SMQ: Acute renal failure (Narrow and Broad), and; Concomitant medication using the WHODD ATC code J01G |
| Long-term cardiovascular effects including changes in lipid profile | 
 SMQ: Dyslipidaemia (Narrow), or; SOC: Cardiac disorders |
| Hypertension with use of concomitant systemic corticosteroids | 
 SMQ: Hypertension (Narrow and Broad), and; Concomitant medication using the WHODD ATC code H02A |
| Renal toxicity | 
 SMQ: Acute renal failure (Narrow and Broad) |
| Hepatic toxicity | 
 SOC: Hepatobiliary disorders, or; HLGT: Hepatobiliary Investigations |
| Malignancies in general | 
 SOC: Neoplasms benign, malignant and unspecified (incl cysts and polyps) |

Abbreviations: AESI, adverse event of special interest; SMQ, Standardized MedDRA Query; ATC, Anatomical Therapeutic Chemical; SOC, System Organ Class; HLGT, High Level Group Term; WHODD, World Health Organization Drug Dictionary

For potentiation of aminoglycoside renal toxicity and hypertension with use of concomitant systemic corticosteroids, the concomitant medications are those started prior to the onset of corresponding AE.

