| Hypocalcemia | Corrected serum calcium of <LLN - 8.0 mg/dL; <LLN - 2.0 mmol/L; Ionized calcium <LLN - 1.0 mmol/L | Corrected serum calcium of <8.0 - 7.0 mg/dL; <2.0 - 1.75 mmol/L; Ionized calcium <1.0 - 0.9 mmol/L; symptomatic | Corrected serum calcium of <7.0 - 6.0 mg/dL; <1.75 - 1.5 mmol/L; Ionized calcium <0.9 - 0.8 mmol/L; hospitalization indicated | Corrected serum calcium of <6.0 mg/dL; <1.5 mmol/L; Ionized calcium <0.8 mmol/L; life-threatening consequences | Death |
| Creatinine increased | >ULN - 1.5 x ULN | >1.5 - 3.0 x baseline; >1.5 - 3.0 x ULN | >3.0 x baseline; >3.0 - 6.0 x ULN | >6.0 x ULN | |
| Hyperglycemia | Abnormal glucose above baseline with no medical intervention | Change in daily management from baseline for a diabetic; oral antidiabetic agent initiated; workup for diabetes | Insulin therapy initiated; hospitalization indicated | Life-threatening consequences; urgent intervention indicated | Death |
| Hypoglycemia | <LLN - 55 mg/dL; <LLN - 3.0 mmol/L | <55 - 40 mg/dL; <3.0 - 2.2 mmol/L | <40 - 30 mg/dL; <2.2 - 1.7 mmol/L | <30 mg/dL; <1.7 mmol/L; life-threatening consequences; seizures | Death |

| AE Term | Grade 1 | Grade 2 | Grade 3 | Grade 4 | Grade 5 |
|------------------|---|--|---|--|---------|
| Hypophosphatemia | <Laboratory finding only and intervention not indicated | Oral replacement therapy indicated | Severe or medically significant but not immediately life-threatening; hospitalization or prolongation of existing hospitalization indicated | life-threatening consequences | Death |
| Hyperkalemia | >ULN - 5.5 mmol/L | >5.5 - 6.0 mmol/L; intervention initiated | >6.0 - 7.0 mmol/L; hospitalization indicated | >7.0 mmol/L; life-threatening consequences | Death |
| Hypokalemia | <LLN - 3.0 mmol/L | <LLN - 3.0 mmol/L; symptomatic; intervention indicated | <3.0 - 2.5 mmol/L; hospitalization indicated | <2.5 mmol/L; life-threatening consequences | Death |
| Hyponatremia | <LLN - 130 mmol/L | 125-129 mmol/L and asymptomatic | 125-129 mmol/L symptomatic; 120-124 mmol/L regardless of symptoms | <120 mmol/L; life-threatening consequences | Death |
| Hypernatremia | >ULN - 150 mmol/L | >150 - 155 mmol/L; intervention initiated | >155 - 160 mmol/L; hospitalization indicated | >160 mmol/L; life-threatening consequences | Death |
| Hyperuricemia | >ULN without physiologic consequences | - | >ULN with physiologic consequences | life-threatening consequences | Death |

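### Under the laboratory rule in both SAPs, a high glucose or uric acid cannot be counted as clinically significant on its value alone, and lipids have no grading row

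*SAP*

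**What the plan says.** Double-blind SAP 7.2 says that "All post-baseline clinical laboratory results will be graded according to CTCAE severity grade", where a scale applies, using the criteria in Appendix 4. For graded parameters, "the CTCAE grades increase from baseline to Grade 2 or higher grade will be considered as clinically significant (CS"). The incidence is summarised in the as-treated population and the values are listed. Open-label SAP 7.2 repeats the rule, with its own Appendix 3, for the population that received ataluren.

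The hyperglycemia row gives Grade 1 as "Abnormal glucose above baseline with no medical intervention" and Grade 2 as "Change in daily management from baseline for a diabetic; oral antidiabetic agent initiated; workup for diabetes". Grade 3 is insulin or hospital admission, and Grade 4 is life-threatening consequences. Hypoglycemia, on the next row, is numeric; its Grade 2 is "<55 - 40 mg/dL; <3.0 - 2.2 mmol/L".

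Total cholesterol, HDL, LDL and triglycerides are in SAP Table 4, but neither appendix has a row for them. The AESI table has a category "Long-term cardiovascular effects including changes in lipid profile", identified from reported event terms (the Dyslipidaemia SMQ or the cardiac SOC).

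Section 7.2 also provides means, mean changes and shift tables for every Table 4 parameter, renal thresholds (Table 5) and liver thresholds in multiples of ULN (Table 6).

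Protocol 9.4.7 asks for two further laboratory summaries: the incidence of the worst CTCAE grade for graded variables, and the frequency of values below, within and above normal for parameters without a CTCAE scale. Neither appears in SAP 7.2, and section 8 of each SAP, which lists changes from the protocol, does not mention their removal.

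**The concern.** Raised glucose and lipids are foreseeable in this trial. Inclusion criterion 6 requires systemic corticosteroids in every boy, and protocol Appendix 1 sets out actions for "Evidence of fasting hyperglycemia". The sponsor itself names lipid change as an event of special interest.

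The table and listing of clinically significant values are where a reader will look for such signals. If the grading scale gives a high glucose no way to reach the threshold, an empty hyperglycemia line says nothing about the data but will be read as reassurance.

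The adverse event tables do not fully make up for this. Protocol 7.1.1 says that laboratory abnormalities needing neither intervention nor further investigation belong to laboratory monitoring and are not adverse events. An untreated rise in glucose or lipids is therefore sent to the laboratory analysis, and that analysis has no threshold for it.

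**Working it through.** No sample size, power or event count is at issue. The check takes each biochemistry entry in SAP Table 4 and asks three things. Does the CTCAE appendix have a row for it? Can a laboratory value alone reach Grade 2 or higher on that row? Does another threshold in 7.2 cover it?

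**Inputs.** Double-blind SAP 7.2 Tables 4 to 6 and Appendix 4; open-label SAP 7.2 and Appendix 3, which match on these rows apart from minor wording; protocol 7.1.1 and 9.4.7.

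| Parameter | Appendix row | Grade 2+ from the value alone | Other threshold in 7.2 |
|---|---|---|---|
| Glucose, high | Yes, no numeric limit | No | None |
| Glucose, low | Yes, numeric | Yes | None |
| Uric acid | Yes; above ULN at Grades 1 and 3, Grade 2 empty, Grade 3 needs consequences | No | None |
| Total cholesterol, HDL, LDL, triglycerides | No | Not graded | None |
| BUN, cystatin C | No | Not graded | Table 5 |
| Creatinine | Yes, numeric | Yes | Table 5, including Grade 1 |
| AST, ALT, bilirubin, alkaline phosphatase | Yes, numeric | Yes | Table 6 |

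**Counts.** Table 4 has 22 biochemistry entries, with bilirubin counted once.

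- No appendix row: bicarbonate, BUN, magnesium, total protein, CK, total cholesterol, LDH, HDL, LDL, triglycerides, cystatin C = 11.
- With a row: 22 − 11 = 11.
- With a row but no value-only Grade 2 or higher on the high side: glucose and uric acid = 2, leaving 11 − 2 = 9 with such a route.
- No row and not covered by Table 5: 11 − 2 (BUN, cystatin C) = 9, of which 4 are lipids.
- No threshold count of any kind for a high value: 9 + 2 = 11 of 22.

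**The rule applied.** A glucose just under 55 mg/dL is Grade 2 hypoglycemia and is counted. A glucose at any multiple of ULN, with no recorded intervention or work-up, is Grade 1 and is not counted. A triglyceride value at any level is not graded, so it is outside the table.

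**Rows without data.** Amylase and lipase have appendix rows but are not in the panel. Hypophosphatemia has a row with non-numeric grades, but phosphorus, although collected under protocol 6.2.9, is not in SAP Table 4. These rows change no result.

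**The case against.** Several stronger readings are tempting, and the documents do not support them.

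- A reader might infer that 7.2 flags values only at Grade 2 or higher. It does not. Table 5 counts renal values, including Grade 1 creatinine, and Table 6 counts liver values in multiples of ULN.
- A reader might infer that lipids will be reported as zero cases. The rule covers only CTCAE-graded parameters, so lipids are absent from the table; they are not a row showing 0.
- A reader might infer a fixed count of 0 of 359 for hyperglycemia. That follows only if grading uses the laboratory value alone. Grade 2 includes a diabetes work-up or an oral agent, and adverse event and concomitant medication data could supply those, although neither SAP says they will. Also, 359 is the ITT count, whereas this incidence uses the as-treated population.
- A reader might infer that rises are hidden altogether. Summary statistics include the maximum (double-blind SAP 4.1, open-label SAP 4.2), shift tables cover every parameter, and abnormalities that needed intervention or investigation are generally reportable as adverse events. Reported dyslipidaemia enters the AESI table.

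It can also be argued that section 8 never withdrew the normal-range frequencies of protocol 9.4.7, so they still apply.

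These points limit the concern but do not remove it. A maximum shows one extreme value, not how many boys passed a limit. The shift-table categories are undefined: by grade, glucose stops at Grade 1 on its value and lipids have none; by normal range, the tables show direction but not size. A summary that the protocol requires and the SAP does not specify may not be produced.

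**Conclusion.** The concern holds for the table and listing of clinically significant values. Followed as written on laboratory values, they cannot flag a high glucose or a high uric acid, and they leave out all 4 lipid parameters. They can flag a low glucose. More broadly, 11 of 22 biochemistry entries have no threshold-based count for a high value. Separately, both SAPs omit two laboratory summaries required by protocol 9.4.7 without declaring it.

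This is a moderate gap in safety reporting. It touches no efficacy endpoint and treats both arms alike, and the underlying data are collected and partly visible elsewhere. It goes beyond missing detail because a stated rule would give a count that is easily misread.

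Two assumptions matter. First, grading uses the laboratory value, which is the natural reading of 7.2 but is not spelled out. Second, no lipid row sits in the two figures that cannot be seen in the available copy of double-blind Appendix 4; open-label Appendix 3 has no such gap and also lacks one.

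**What to change.** In section 7.2 and the CTCAE appendix of both SAPs:

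1. For high glucose, uric acid and lipids, do not rely on the non-numeric or absent grades. Prespecify numeric laboratory reporting limits, for example multiples of ULN as Table 6 uses for liver tests, and state for HDL which side is reported. Count and list values beyond those limits by arm. The documents give no cut-offs for these parameters, so the sponsor must choose and justify them. They are reporting limits only and leave the protocol's management rules untouched.
2. Restore the worst-grade incidence and the below/within/above-normal frequencies of protocol 9.4.7, or list their removal in section 8.
3. Label additions to the double-blind period as post hoc, since open-label SAP section 1 dates that lock to 11 April 2022. The on-ataluren period starts at the first ataluren dose, so for the early-start group it includes those locked data and needs the same label for that part.

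The cost is SAP text and a small programming change on values already collected. The safety tables may then show more abnormalities than they would under the present rule.

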3.2 Inclusion Criteria

Subjects must meet all of the following conditions to be eligible for enrollment into the study:

1. Evidence of signed and dated informed consent/assent document(s) indicating that the subject (and/or his parent/legal guardian) has been informed of all pertinent aspects of the trial. ***Note: If the study candidate is considered a child under local regulation, a parent or legal guardian must provide written consent prior to initiation of study screening procedures and the study candidate may be required to provide written assent. The rules of the responsible institutional review board/ethics committee (IRB/EC) regarding whether one or both parents must provide consent and the appropriate ages for obtaining consent and assent from the subject should be followed.***
2. Male sex.
3. Age ≥ 5 years. When Version 3 is implemented or approximately 270 subjects have enrolled in the study, only subjects aged ≥ 7 to ≤ 16 who meet the mITT criteria will be eligible to enroll.
4. Phenotypic evidence of DMD based on the onset of characteristic clinical symptoms or signs (eg, proximal muscle weakness, waddling gait, and Gowers' maneuver) by 6 years of age and an elevated serum creatine kinase (CK). ***Medical documentation of phenotypic evidence of DMD needs to be provided upon request by the PTC Therapeutics medical monitor.***
5. Documentation of the presence of a nonsense point mutation in the dystrophin gene as determined by gene sequencing. ***Note: Review and approval of documentation by sponsor or designee is required prior to enrollment.***

6. Use of systemic corticosteroids (prednisone/prednisolone or deflazacort) for a minimum of 12 months immediately prior to start of study treatment, with no significant change in dosage or dosing regimen for a minimum of 3 months immediately prior to start of study treatment and a reasonable expectation that dosage and dosing regimen will not change significantly for the duration of the study. **Note: Daily, every other day, high-dose weekend, and intermittent regimens permitted only. The doses recommended or required are shown in Table 1. Increases in corticosteroid dose to adjust for increases in body weight will not exclude a subject from participation.**

Table 1. Corticosteroid Regimens and Doses Recommended or Required

Regimen	Prednisone/Prednisolone	Deflazacort
Daily	0.75 mg/kg (recommended) At least 0.3 mg/kg (required)	0.9 mg/kg (recommended) At least 0.3 mg/kg (required)

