5.3.2 Evaluation of Adverse Events or Laboratory Abnormalities

The PTC Therapeutics medical monitor or designee should be notified of any AE or laboratory abnormality that leads to dose interruption and should be apprised of ancillary laboratory or other diagnostic findings and the evolving data from any work-up of the initial abnormality.

Clinical evaluations for potential hepatic and renal toxicities may include the following:

- **Hepatic:** The medical history, hepatitis screening results, all clinical blood values (particularly serum bilirubin, gamma-glutamyl transferase [GGT], aspartate aminotransferase [AST], and alanine aminotransferase [ALT] values), and all concomitant medications should be reviewed. Depending upon changes observed, the recommended diagnostic workup may include more frequent monitoring or further evaluations for viral hepatitis and immune disorders; tests for cholelithiasis; or abdominal ultrasound, computed tomography, MRI, or other imaging methods.
- **Renal:** The medical history, all clinical blood and urine renal values, serum electrolytes, medications, and potential pre or- post renal conditions should be reviewed. Depending upon the changes observed, recommended diagnostic workup may include further evaluations of blood or urine; tests of glomerular filtration rate, concentrating ability, or other renal functions; computed tomography, MRI, or other imaging methods; and/or renal biopsy.

5.3.3 Instructions for Resuming Study Drug Administration after an Interruption for Safety Concerns

In deciding whether to re-institute study drug after a dose interruption for any clinically significant safety concern, the investigator in consultation with PTC Therapeutics should consider factors such as the following:

- Type and severity of the AE or laboratory abnormality
- The potential causal relationship of study drug
- The subject's status in terms of DMD and other health conditions
- The ability to monitor for recurrence of the event

If further evaluation reveals that the AE that led to dose interruption was not related to the study drug, study drug may be restarted.

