Laboratory abnormality related to elevated liver function test will also be summarized for all post-baseline assessments according to [Table 6](#).

Table 6: Criteria for Elevated Liver Function Test

| Category | Criteria |
|-------------------------------|---|
| Elevated Aminotransferases | 
 ALT >3xULN AST >3xULN ALT or AST >3xULN |
| Elevated Bilirubin | 
 Total Bilirubin >2xULN AST or ALT >3xULN and Total Bilirubin >2xULN |
| Elevated Alkaline Phosphatase | 
 AP >1.5xULN AST or ALT >3xULN, Total Bilirubin >2xULN, and AP >1.5xULN |

Abbreviations: ALT = alanine aminotransferase; AST = aspartate aminotransferase; AP = alkaline phosphatase; ULN = upper limit of normal.

A listing of all CS abnormal laboratory values, renal laboratory abnormal values, and elevated liver function test will be provided.

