APPENDIX 4. LABORATORY RELATED CTCAE SEVERITY GRADE

[figure not shown]
[figure not shown]

| AE Term | Grade 1 | Grade 2 | Grade 3 | Grade 4 | Grade 5 |
|---|---|--|--|--|----------------|
| White blood cell decreased | <LLN - 3000/mm ³ ; <LLN - 3.0 x 10 ⁹ /L | <3000 - 2000/mm ³ ; <3.0 - 2.0 x 10 ⁹ /L | <2000 - 1000/mm ³ ; <2.0 - 1.0 x 10 ⁹ /L | <1000/mm ³ ; <1.0 x 10 ⁹ /L | |
| White blood cell increased (leukocytosis) | - | - | >100,000 mm ³ | Clinical manifestations of leucostasis; urgent intervention indicated | Death |
| Anemia | Hemoglobin (Hgb) <LLN - 10.0 g/dL; <LLN - 6.2 mmol/L; <LLN - 100 g/L | Hgb <10.0 - 8.0 g/dL; <6.2 - 4.9 mmol/L; <100 - 80g/L | Hgb <8.0 g/dL; <4.9 mmol/L; <80 g/L; transfusion indicated | Life-threatening consequences; urgent intervention indicated | Death |
| Lymphocyte count decreased | <LLN - 800/mm ³ ; <LLN - 0.8 x10 ⁹ /L | <800 - 500/mm ³ ; <0.8 - 0.5 x 10 ⁹ /L | <500 - 200/mm ³ ; <0.5 - 0.2 x 10 ⁹ /L | <200/mm ³ ; <0.2 x 10 ⁹ /L | |
| Lymphocyte count increased | - | >4000 - 20,000 mm ³ | >20,000 mm ³ | - | |
| Platelet count decreased | <LLN - 75,000/mm ³ ; <LLN - 75.0 x 10 ⁹ /L | <75,000 - 50,000/mm ³ ; <75.0 - 50.0 x 10 ⁹ /L | <50,000 - 25,000/mm ³ ; <50.0 - 25.0 x 10 ⁹ /L | <25,000/mm ³ ; <25.0 x 10 ⁹ /L | |
| Serum amylase increased | >ULN - 1.5 x ULN | >1.5 - 2.0 x ULN; >2.0 - 5.0 x ULN and asymptomatic | >2.0 - 5.0 x ULN with signs or symptoms; >5.0 x ULN and asymptomatic | >5.0 x ULN and with signs or symptoms | |
| Alkaline phosphatase increased | >ULN - 2.5 x ULN if baseline was normal; 2.0 - 2.5 x baseline if baseline was abnormal | >2.5 - 5.0 x ULN if baseline was normal; >2.5 - 5.0 x baseline if baseline was abnormal | >5.0 - 20.0 x ULN if baseline was normal; >5.0 - 20.0 x baseline if baseline was abnormal | >20.0 x ULN if baseline was normal; >20.0 x baseline if baseline was abnormal | |
| Alanine aminotransferase increased | >ULN - 3.0 x ULN if baseline was normal; 1.5 - 3.0 x baseline if baseline was abnormal | >3.0 - 5.0 x ULN if baseline was normal; >3.0 - 5.0 x baseline if baseline was abnormal | >5.0 - 20.0 x ULN if baseline was normal; >5.0 - 20.0 x baseline if baseline was abnormal | >20.0 x ULN if baseline was normal; >20.0 x baseline if baseline was abnormal | |

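### Table 6 in both SAPs cannot tell pre-dose from new ALT/AST elevations, and no planned summary pairs a baseline-referenced enzyme or GGT with bilirubin

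*SAP*

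**What the plan says.** **Table 6 (section 7.2 of both SAPs).** The lead-in reads "Laboratory abnormality related to elevated liver function test will also be summarized for all post-baseline assessments according to" Table 6. The rows are ALT and AST above 3 x ULN singly, "ALT or AST >3xULN", total bilirubin above 2 x ULN alone, "AST or ALT >3xULN and Total Bilirubin >2xULN", alkaline phosphatase (AP) above 1.5 x ULN, and all three together. No row refers to baseline, and GGT does not appear.

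**Other laboratory summaries in the same section.** Table 4 includes "aspartate aminotransferase, alanine Aminotransferase, gamma glutamyl Transferase, creatine kinase, alkaline phosphatase". For these parameters the double-blind SAP plans mean change and "shift tables for each laboratory parameters from baseline to each of the post-baseline visit". The open-label SAP does likewise from the on-ataluren baseline. Both also count rises in CTCAE grade from baseline to Grade 2 or higher. The grading appendix (Appendix 4 double-blind, Appendix 3 open-label) puts Grade 2 for ALT and AST at ">3.0 - 5.0 x ULN if baseline was normal; >3.0 - 5.0 x baseline if baseline was abnormal". GGT is graded the same way, with Grade 2 starting above 2.5 times ULN or baseline.

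**Protocol.** Section 3.2, item 4, requires raised CK at entry. Section 3.3 names hepatitis B and C serology but lists no ALT or AST limit; item 12 leaves other laboratory abnormalities to the investigator's judgement. Section 5.3.2 lists, for hepatic evaluation, "particularly serum bilirubin, gamma-glutamyl transferase [GGT], aspartate aminotransferase [AST], and alanine aminotransferase [ALT] values".

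**The concern.** A fixed ULN cut-off applied after baseline works as a drug-safety screen when few subjects exceed it beforehand. Nothing at entry ensures that here. Protocol section 1.1 describes muscle membranes that tear on contraction, and entry requires raised CK. It is therefore plausible, though the documents do not say so, that ALT and AST are also raised before dosing. Whatever the source, a pre-existing elevation enters Table 6 as a post-baseline event.

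Two things are at stake. The ALT/AST rows lose contrast between arms as the background rises. The combined rows, which are the only planned summaries joining enzymes to bilirubin, lose their enzyme half for boys already above the cut-off. This matters most in the open-label SAP (section 7), where safety is summarised over time on ataluren only, so no concurrent placebo group shows the background.

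**Working it through.** The plan attaches no rate, power or sample size to the liver criteria, so there is no figure of its own to reproduce.

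**1. Logic of the combined rows.** Let A = ALT or AST above 3 x ULN, B = total bilirubin above 2 x ULN, P = AP above 1.5 x ULN. If A is true for a boy at every visit, then (A and B) = B, and (A and B and P) = (B and P). The enzyme term adds nothing for him.

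**2. Table 6 beside the CTCAE route.** With an abnormal baseline, Grade 2 for ALT starts above 3 x baseline.

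| Baseline ALT | Table 6 ALT row if unchanged | Grade 2 starts above |
|---|---|---|
| 0.9 x ULN | not met | 3 x ULN |
| 2 x ULN | not met | 3 x 2 = 6 x ULN |
| 5 x ULN | met at every visit | 3 x 5 = 15 x ULN |
| 10 x ULN | met at every visit | 3 x 10 = 30 x ULN |

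A boy who goes from 10 to 25 x ULN reaches 25/10 = 2.5 x baseline. That is below the Grade 2 limit, so he is not counted as clinically significant, and in Table 6 he looks the same as before dosing.

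**3. Illustration of dilution.** Inputs:
- 359 in the ITT population (open-label SAP 6.2.1; changes document 3.1.1), so 359/2, about 180 per arm. The as-treated number is not given.
- b = share above 3 x ULN without liver injury. Assumed.
- h = true hepatic excess on ataluren, independent of b. Assumed.

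Flag rates are b on placebo and b + (1 - b)h on ataluren. Power is for a two-sided 0.05 comparison of two proportions, counting rejections in the direction of an ataluren excess. No such test is planned; power serves only as a yardstick for separation.

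| b | Flagged, placebo vs ataluren, h = 10% | Power, h = 10% | Power, h = 5% |
|---|---|---|---|
| 5% | 9.0 vs 26.1 | 0.86 | 0.41 |
| 25% | 45.0 vs 58.5 | 0.35 | 0.12 |
| 50% | 90.0 vs 99.0 | 0.16 | 0.07 |
| 70% | 126.0 vs 131.4 | 0.09 | 0.05 |
| 90% | 162.0 vs 163.8 | 0.05 | 0.04 |

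Example for b = 50%, h = 10%: 180 x (0.50 + 0.50 x 0.10) = 99.0.

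If a baseline-relative or GGT criterion brought the background to 1% and still caught the same excess, power would be about 0.98 (h = 10%) or 0.73 (h = 5%). That is an upper case: a 3 x baseline limit would miss some true rises, as step 2 shows.

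**4. What each planned summary can show.**

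| Summary | Baseline-referenced | Includes GGT | Paired with bilirubin |
|---|---|---|---|
| Table 6 | no | no | yes, with ALT/AST |
| Mean change, shift tables | yes | yes | no |
| CTCAE rise to Grade 2 or higher | yes | yes | no |
| Hepatic AESI | depends on AE reporting | through reported terms | no |

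No row is both baseline-referenced and paired with bilirubin, and none pairs GGT with bilirubin.

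**The case against.** The strongest reply is that Table 6 is a supplement. The same section plans change from baseline, shift tables and baseline-relative CTCAE incidence for ALT, AST and GGT. A multiple-of-baseline ALT/AST count and a GGT count at the Grade 2 limit therefore already exist singly. This stands, and it narrows the point to baseline visibility in Table 6 and the pairing with bilirubin. The cover is only partial. The Grade 2 limit is coarse when baseline is high. The shift-table categories are not stated for these parameters; if they are normal/high, a boy who is high throughout shows no shift.

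It can also be said that the reduction to bilirubin costs specificity, not sensitivity, because a boy with real injury and raised bilirubin is still flagged. That is correct. Randomisation also balances the background on average in the double-blind period, so the effect there is dilution, not bias.

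Three stronger readings might be inferred, and the documents do not support them:
- **That most boys in both arms will be flagged.** No baseline ALT or AST distribution is given. Raised CK makes a background plausible but does not size it.
- **That a true liver signal will be masked.** The baseline-referenced summaries above, the bilirubin-alone row and CTCAE-graded GGT all remain.
- **That the hepatic AESI is compromised.** It is defined by MedDRA terms (double-blind SAP 7.1.1, open-label SAP 7.1.2), not by Table 6. Nor does it replace a laboratory screen, since protocol 7.1.1 keeps laboratory abnormalities needing no intervention or further investigation out of AE reporting.

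Table shells are held in a separate document, so a baseline column may already be intended.

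**Conclusion.** The point holds for Table 6 only. In both SAPs it counts elevations that pre-date dosing as post-baseline liver abnormalities. Its combined rows lose their enzyme component for boys already above 3 x ULN, and it leaves out GGT, which the protocol names for hepatic evaluation and the SAPs already summarise and grade.

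The size is unknown because the share of boys affected is not in the documents. On the assumed rates, separation in the ALT/AST row is already poor at a 25% background (0.35 for a true 10% excess), so the point does not need a majority of boys to be affected. If the background is small, the present table works adequately and the additions change little.

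This is a descriptive safety summary, so the weight is minor to moderate. It matters most for the on-ataluren summaries.

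**What to change.** Keep the current Table 6 rows in both SAPs as background and add, by treatment group:

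- **(a)** the number already meeting each criterion at baseline, using the on-ataluren baseline in the open-label SAP;
- **(b)** treatment-emergent counts among boys who did not meet the ULN criterion at baseline;
- **(c)** for boys with ALT or AST above ULN at baseline, a multiple-of-baseline row paired with total bilirubin above 2 x ULN. State the multiple beforehand; the appendix already supplies 1.5 x baseline (start of Grade 1) and 3 x baseline (start of Grade 2);
- **(d)** a GGT row at the appendix Grade 2 limit, alone and paired with total bilirubin above 2 x ULN.

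Rows (b) and (c) belong together: (b) alone would drop the boys at issue, and (c) picks them up. Row (c) would still miss a hepatic rise in a boy whose ALT or AST has fallen since baseline, which is a further reason for (d).

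The double-blind data were soft-locked on 11 April 2022 (open-label SAP section 1), so label the additions as supplementary descriptive safety summaries. They use data already collected. The cost is a slightly longer table in each report, with no effect on alpha, the primary analysis or the AESI definition.
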